7.2.3 Serious Adverse Events (SAEs)

All SAEs, regardless of attribution, occurring from time of signed informed consent, through 56 days after the last administration of study drug, must be reported upon discovery or occurrence.

An SAE is defined in regulatory terminology as any untoward medical occurrence that:

- **Results in death.**

If death results from (progression of) the disease, the disease should be reported as event (SAE) itself.

- **Is *life-threatening*.**
The patient was at risk of death at the time of the event; it does not refer to an event that hypothetically might have caused death if it were more severe.
- **Requires *in-patient hospitalization or prolongation of existing hospitalization for ≥ 24 hours.***
- Results in ***persistent or significant disability or incapacity*.**
- Is a ***congenital anomaly/birth defect*.**
- Is an ***important medical event*** not consistent with the risk information described in the general investigational plan or elsewhere in the current IND, and the event is not anticipated from the subject's disease history or status.
- **Any significant new neurological deficit in the post-operative period (within 7 days), will be considered an SAE.** For study patients with a history of seizures prior to entry, a single seizure will be considered an AE, but not an SAE. An increase in the seizure frequency or severity in such patients will be considered an SAE
- Secondary malignancy, or
- Any event in which the severity or specificity is
- Any event that does not meet the above criteria, but that in the judgment of the investigator jeopardizes the patient, may be considered for reporting as a serious adverse event. The event may require medical or surgical intervention to prevent one of the outcomes listed in the definition of "Serious Adverse Event." For example: allergic bronchospasm requiring intensive treatment in an emergency room or at home; convulsions that may not result in hospitalization; development of drug abuse or drug dependence.

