7.3.3 Expedited Reporting of SAEs/Other Events

7.3.3.1 Reporting to the Northwestern University QAM/DMC

All SAEs must be reported to the assigned QAM within 24 hours of becoming aware of the event. Completion of the NU CRO SAE Form, provided as a separate document, is required.

The completed form should assess whether or not the event qualifies as a UPIRSO. The report should also include:

- Protocol description and number(s)
- The patient's identification number
- A description of the event, severity, treatment, and outcome (if known)
- Supportive laboratory results and diagnostics
- The hospital discharge summary (if available/applicable)

All SAEs will be reported to, and reviewed by, the DMC at their next meeting.

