8.1.10 Side effects

Toxicities Associated with Adenoviral Injection

In previous trials of intratumoral adenoviral injection, toxicity was rare, and overall, the approach has been well tolerated. A summary of grade 3 and 4 toxicities seen in the previous trials is provided in **Table 8** below. In the Phase I study in recurrent brain

tumors, CNS toxicity (lethargy, confusion, grade 3 hyponatremia, fever, leukocytosis, intratumoral hemorrhage in 1, hydrocephalus in the other) was observed in 2/2 patients at 2×10^{12} vp dose level. In the lower dose levels, no DLTs were observed but transient and less severe events included seizure, small intratumoral hemorrhage, worsening of neurologic symptoms, mild hyponatremia. One patient at the highest dose level in the prostate dose escalation study experienced grade 4 transient thrombocytopenia which was considered a DLT and also transient grade 3 elevation in liver transaminases.

Table 8 – Summary of Grade 3 and 4 Toxicities In Trials With Adenovirus		
Patient Characteristics	Treatment Specifics	Toxicity
Recurrent malignant gliomas IND 6371 13 patients Trask et al, 2000	Dose escalation: 2×10^9 vp, (2 pts) 2×10^{10} vp, (2 pts) 2×10^{11} vp, (7 pts) 2×10^{12} vp, (2 pts) Delivery: Stereotactic injection Prodrug: GCV Concurrent tx: none	CNS toxicity in 2/2 patients at 2×10^{12} vp dose level Therapy tolerated by other 11 patients including 7/7 patients treated at 2×10^{11} vp
Recurrent ovarian cancer, stage IIIC IND 7311 10 patients Hasenburg et al, 2001	Dose escalation: 2×10^{10} vp, (2 pts) 2×10^{11} vp, (2 pts) 2×10^{12} vp, (2 pts) 2×10^{13} vp, (4 pts) Delivery: Intraperitoneal Prodrug: ACV or Valacyclovir Concurrent tx: Topotecan	No significant toxicity attributable to gene therapy.
Recurrent prostate cancer IND 6636 18 patients Herman et al, 1999	Dose escalation: 2×10^9 vp, (4 pts) 2×10^{10} vp, (5 pts) 2×10^{11} vp, (4 pts) 2×10^{12} vp, (5 pts) Delivery: Intraprostatic Prodrug: GCV Concurrent tx: none	One patient at 2×10^{12} vp dose level had transient grade 4 thrombocytopenia and grade 3 hepatotoxicity
Recurrent prostate cancer (radiation failures), multiple injections 27 patients (18 new patients plus 9 additional injections in patients from first study) Shalev et al, 2000; Miles et al, 2001	Dose: $2-6 \times 10^{11}$ vp Delivery: Intraprostatic Prodrug: GCV Concurrent tx: none	Grade 3 hypertension in one patient requiring anti-hypertensive therapy

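### Section 7.2.3 contradicts itself for a single seizure of usual severity that leads to hospitalisation in a patient with seizure history: the general criteria make it an SAE, the seizure exemption does not

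*Combined protocol and SAP*

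**What the plan says.** The definition in Section 7.2.3 opens broadly: "An SAE is defined in regulatory terminology as any untoward medical occurrence that", followed by a list in which any one item suffices. Two items matter here. One is the life-threatening criterion, explained as "The patient was at risk of death at the time of the event". The other is "in-patient hospitalization or prolongation of existing hospitalization for ≥ 24 hours".

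Further down, the item on new neurological deficits in the first seven post-operative days carries two sentences on seizures. The first is the exemption: "For study patients with a history of seizures prior to entry, a single seizure will be considered an AE, but not an SAE". The second limits it: "An increase in the seizure frequency or severity in such patients will be considered an SAE".

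The closing item leaves other events to the investigator's judgment and gives as one example "convulsions that may not result in hospitalization".

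The classification has direct consequences. Section 7.3.3.1 states: "All SAEs must be reported to the assigned QAM within 24 hours of becoming aware of the event", and sends all SAEs to the DMC. Section 7.3.3.4 includes SAE data in the quarterly reports to the cell provider. Section 10.3.3 plans a separate SAE listing.

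**The concern.** The exemption has no proviso. For a patient with previous seizures, one seizure that prolongs the post-operative stay by a day or more is serious under the hospitalisation item and not serious under the exemption. Two investigators, or one investigator on two occasions, could classify the same event differently and each cite the protocol.

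The situation is foreseeable. Under Sections 4.8 and 4.9, patients stay in hospital after the procedure and are seen on days 1 to 3 as inpatients, so prolongation of an existing stay is a natural consequence of an early seizure. The account of previous adenoviral injection into brain tumours in Section 8.1.10 notes, at the lower dose levels, that "transient and less severe events included seizure, small intratumoral hemorrhage, worsening of neurologic symptoms". The temozolomide side-effect list under Section 8.2 puts convulsions among reactions with an incidence of at least 10%. Temozolomide starts 10 to 14 days after injection, inside the 56-day SAE window. That figure covers neither serious seizures specifically nor patients with seizure history, but it shows that seizures are not remote.

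What is at stake is consistent safety reporting. Dose levels of three to six patients are compared descriptively, so whether a neurological event counts as serious should not depend on which sentence is applied.

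**Working it through.** The documents give no figure that depends on this definition, so there is nothing to recompute. The check is to run each type of seizure, in a patient with seizure history, through the three rules: the general criteria, the exemption, and the sentence on increased frequency or severity.

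1. **Single seizure, usual severity, no general criterion met.** The general criteria do not apply and the exemption does. AE only; no conflict.
2. **Single seizure more severe than before.** The sentence on increased severity makes it an SAE. This would ordinarily cover a life-threatening seizure.
3. **Seizures more frequent than before.** The sentence on increased frequency makes them an SAE.
4. **Single seizure, no more severe or frequent than before, leading to hospitalisation or prolongation of at least 24 hours.** SAE under the hospitalisation item; not an SAE under the exemption; not reached by the sentence on increase. Unresolved. A life-threatening seizure judged no worse than the patient's previous ones belongs here too, but should be rarer.

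Only case 4 is a contradiction. The sentence on increase does not settle it, because severity and seriousness are different attributes. The protocol itself grades severity in Section 7.2.2 and defines seriousness separately in Section 7.2.3. A seizure can be of usual severity and still keep a patient in hospital.

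The boundary of case 4 is also soft. No reference period is given for an increase, and the study calendar (Table 5) has medical history and a neurological examination but no item for baseline seizure frequency or severity. One seizure in a previously controlled patient could be taken as an increase or as the exempt event.

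The closing item adds an awkward contrast. A convulsion that does not lead to hospitalisation may be reported as serious on judgment, while a single seizure that does lead to it is exempt, on the literal reading, if the patient has seizure history.

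Tracing where the SAE flag is used:

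- **Uses the flag:** the 24-hour report to the QAM and DMC review of SAEs (7.3.3.1), FDA reporting (7.3.3.3), SAE data to the cell provider (7.3.3.4) and the SAE listing (10.3.3).
- **Does not use the flag:** the dose-limiting toxicity definition, which rests on CTCAE grade and attribution (4.2.1); the pause rule, which counts life-threatening or fatal neurological toxicity (10.3.2.2); and the listing and tabulation of all AEs (10.3.3).

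**The case against.** The strongest reply is that the list is disjunctive and the seizure sentences sit inside the item on post-operative neurological deficit. On that reading they only say that an isolated seizure in such a patient does not qualify under that item, and the death, life-threatening and hospitalisation items apply independently. This reading is available. It is not compelled: the exemption is worded as a flat statement that the event is not an SAE, and the sentence after it creates an SAE category of its own that is not tied to a new deficit or to the seven-day window. The text supports both readings and ranks neither.

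A reader might infer something stronger: that a single seizure can never be serious in these patients, so serious seizures as a class vanish from the SAE count. The documents do not support that. The sentence on increased frequency or severity brings most of the worst events back in, the closing item shows that seizures are not treated as categorically non-serious, and loss from the count follows from only one of the two readings.

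It is also fair to say that oversight does not rest on SAEs alone. Section 7.3.1 has the DMC review routine AEs, and Section 7.0 has the safety board review complications of the therapy before new patients enrol. The text of Section 7.3.3.3 limits expedited FDA reports to associated and unexpected events. Under Section 7.3.2, a seizure of usual severity would often count as expected, since seizures are named in the protocol. Table 6 does not repeat those qualifiers for events leading to hospitalisation, so this reduces the consequence without removing it.

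**Conclusion.** The contradiction is real and narrow. It concerns one event type: a single seizure, no worse or more frequent than before, in a patient with seizure history, that nonetheless meets a general seriousness criterion, mainly hospitalisation or prolongation of at least 24 hours. This is a stated rule in conflict with the definition around it, not a missing detail.

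On the literal reading, such an event misses the 24-hour report, the DMC's SAE review and the SAE listing. It remains a recorded AE, and dose escalation and the pause rule are unaffected.

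Its frequency cannot be estimated from the documents. They give neither the share of patients with seizure history nor a rate of seizures leading to hospitalisation, and any projected count would also have to exclude events already covered by the sentence on increase. The only arithmetic available is that one event classified differently moves a dose level's SAE proportion by 1/6 = 17 to 1/3 = 33 percentage points. That is true of any single event in groups of six or three and says nothing about how often this one would occur.

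**What to change.** Reconcile the sentences in Section 7.2.3 by stating the order of precedence: in a patient with seizure history, the single-seizure exemption applies only when the seizure meets none of the other listed seriousness criteria. Keep the sentence that makes an increase in frequency or severity an SAE.

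This preserves the evident aim of not reporting routine seizures as serious, makes classification reproducible across arms and dose levels, and changes nothing in treatment or in the escalation rules. The cost is one clause in an amendment and slightly more SAE reports.

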7.2.4 Unanticipated Problems Involving Risks to Subject or Others

Any incident, experience or outcome that meets **all** of the following criteria:¹

- a. Unexpected (in terms of nature, severity, or frequency) given the following:
 - (1) The research procedures described in the protocol-related documents such as the IRB approved research protocol, informed consent document or Investigators Brochure (IB); and
 - (2) The characteristics of the subject population being studied; and is
- b. Related or possibly related to participation in the research (possibly related means there is a reasonable possibility that the incident, experience, or outcomes may have been caused by the drugs, devices or procedures involved in the research); and
- c. Suggests that the research places subjects or others at a greater risk of harm (including physical, psychological, economic, or social harm) than previously known or recognized

7.2.4.1 Unanticipated Problems that ARE Adverse Events

Adverse events are any untoward or unfavorable medical occurrence in a human subject, including any abnormal sign (for example, abnormal physical exam or laboratory finding), symptom, or disease, temporally associated with the subject's participation in the research.

7.2.4.2 Unanticipated Problems that ARE NOT Adverse Events

Unanticipated problems that do not fit the definition of an adverse event, but which may, in the opinion of the investigator, involve risk to the subject, affect others in the research study, or significantly impact the integrity of research data. For example, report occurrences of breaches of confidentiality, accidental description of study records, unaccounted for study drug, or black box warnings issued by the FDA. This also includes

unplanned protocol deviations/violations that have already occurred, that may adversely affect the rights, safety or welfare of the research participants, AND for which you did not seek IRB approval.

7.2.4.3 Unanticipated Problems that ARE Adverse Events

Adverse events are any untoward or unfavorable medical occurrence in a human subject, including any abnormal sign (for example, abnormal physical exam or laboratory finding), symptom, or disease, temporally associated with the subject's participation in the research.

7.2.4.4 Unanticipated Problems that ARE NOT Adverse Events

Unanticipated problems that do not fit the definition of an adverse event, but which may, in the opinion of the investigator, involve risk to the subject, affect others in the research study, or significantly impact the integrity of research data. For example, report occurrences of breaches of confidentiality, accidental description of study records, unaccounted for study drug, or black box warnings issued by the FDA. This also includes unplanned protocol deviations/violations that have already occurred, that may adversely affect the rights, safety or welfare of the research participants, AND for which you did not seek IRB approval.

7.3 Adverse Event Reporting

7.3.1 Routine Reporting

All routine adverse events, such as those that are expected, or are unlikely or definitely not related to study participation, are to be reported on the appropriate eCRF. Routine AEs will be reviewed by the Data Monitoring Committee (DMC) according to the study's phase and risk level, as outlined in the DSMP.

7.3.2 Determining if Expedited Reporting is Required

This includes all events that occur within 56 days of the last dose of protocol treatment. Any event that occurs more than 56 days after the last dose of treatment and is attributed (possibly, probably, or definitely) to the agent(s) must also be reported accordingly.

- 1) Identify the type of adverse event using the NCI CTCAE v 4.03.
- 2) Grade the adverse event using the NCI CTCAE v 4.03.
- 3) Determine whether the adverse event is related to the protocol therapy.
Attribution categories are as follows:
 - Definite: AE is clearly related to the study treatment.
 - Probable: AE is likely related to the study treatment.
 - Possible: AE may be related to the study treatment.
 - Unlikely: AE not likely to be related to the study treatment.
 - Unrelated: AE is clearly NOT related to the study treatment.
- 4) Determine the prior experience of the adverse event.
Expected events are those that have been previously identified as resulting from administration of the agent. An adverse event is considered unexpected, for expedited reporting purposes only, when either the type of event or the severity of the event is not listed in:
 - the current protocol
 - the drug package insert
 - the current Investigator's Brochure

7.3.3 Expedited Reporting of SAEs/Other Events

7.3.3.1 Reporting to the Northwestern University QAM/DMC

All SAEs must be reported to the assigned QAM within 24 hours of becoming aware of the event. Completion of the NU CRO SAE Form, provided as a separate document, is required.

The completed form should assess whether or not the event qualifies as a UPIRSO. The report should also include:

- Protocol description and number(s)
- The patient's identification number
- A description of the event, severity, treatment, and outcome (if known)
- Supportive laboratory results and diagnostics
- The hospital discharge summary (if available/applicable)

All SAEs will be reported to, and reviewed by, the DMC at their next meeting.

7.3.3.2 Reporting to the Northwestern University IRB

- Any death of an NU subject that is unanticipated in nature and at least possibly related to study participation will be promptly reported to the NU IRB within 24 hours of notification.
- Any death of an NU subject that is actively on study treatment (regardless of whether or not the event is possibly related to study treatment)
- Any death of a non-NU subject that is unanticipated and at least possibly related and any other UPIRSOs will be reported to the NU IRB within 5 working days of notification.
- All other deaths of NU subjects not previously reported, other non-NU subject deaths that were unanticipated and unrelated, and any other SAEs that were not previously reported as UPIRSOs will be reported to the NU IRB at the time of annual continuing review.

7.3.3.3 Reporting to the FDA

The FDA will be notified within 7 calendar days of any SAE that is associated with study treatment, is unexpected, and is fatal or life-threatening.

The FDA will be notified within 15 calendar days of any SAE that is associated with the study treatment, unexpected, and serious but *not fatal or life-threatening*. This includes any previous SAEs that were not initially deemed reportable, but are later determined to meet the criteria for reporting (i.e. by the DMC).

All other SAEs will be reported on an annual basis as part of the annual FDA report.

Table 6 summarizes event reporting.

Table 6 – Adverse Event Reporting			
Type of Event	Timing of Report*		
	IRB	IBC (COMS)	FDA and NIH OBA
Fatal or life threatening	As soon as possible, No later than 7 calendar days	As soon as possible, no later than 7 calendar days	As soon as possible. No later than 7 calendar days
SAE resulting in one of the following:			
1. Inpatient hospitalization or prolongation of hospitalization	As soon as possible, no later than 15 calendar days	As soon as possible, no later than 15 calendar days	As soon as possible, no later than 15 calendar days
2. A persistent or significant disability or incapacity			
3. A congenital anomaly or birth defect			

Any other unexpected adverse experiences associated with the use of the product	According to institutional requirements	According to institutional requirements	In the annual report
---	---	---	----------------------

7.3.3.4 Quarterly IND Reports

Reports containing the following information will be sent on a quarterly basis to City of Hope, the provider of the NSCs:

- Enrollment Information
- Demographics
- Interim Results on the progress toward identifying the MTD
- AE and SAE Data (unlikely, possibly, probably, definitely related)

8.0 DRUG INFORMATION

8.1 Agent NSC-CRAd-S-pk7

8.1.1 Other names- none

8.1.2 Classification- NA

8.1.3 Mode of action

This cell product is an oncolytic vector, CRAd-Survivin-pk7 (CRAd-S-pk7), for the treatment of malignant gliomas. CRAd-S-pk7 is a chimeric vector containing a pk7 fiber modification and a survivin promoter driving E1A replication. CRAd-S-pk7 vector effectively replicates in many glioma cell lines like U-87MG, U-251MG, A172, Kings-1, No. 10 and U-118MG and leads to tumor oncolysis in these cell lines with minimal viral replication and toxicity in normal human brain.

8.1.4 Storage and stability

The HB1.F3.CD_CRAd-S-pk7 cell product suspended in CryoStor 10 was vialled using a volume of 1.3 ml/vial at a concentration of 2.5×10^7 per ml (3.25×10^7 cells per vial). CryoStor cryopreservation freeze media products have been designed to mitigate temperature-induced molecular cell stress responses during freezing and thawing. All CryoStor products are pre-formulated with USP grade DMSO, a permeant solute cryoprotective agent which helps mitigate damage from the formation of intracellular ice. CryoStor products meet USP <71> Sterility and USP <85> Endotoxin testing standards, and are manufactured under cGMP. The final product has a pH of 8.0 and is a translucent, colorless liquid with no particulates.

The HB1.F3.CD_CRAd-S-pk7 cell product is stored in vapor phase liquid nitrogen at $\leq -140^{\circ}\text{C}$ in CryoStor 10 freezing medium. Previous qualification assays performed on the cell product confirm that cells are viable for up to six hours at room temperature. The stability testing plan for the HB1.F3.CD.CRAd-S-pk7 product is described in **Table 7** below.

Table 7 – Stability Testing Plan

Test	Specification	0 month	4 month	12 months June 2016	24 months June 2017
Flow cytometry nestin	Report Results	86% positive (98.5% prior to infection) UAB QC-778	85% positive UAB QC-868	X	X
Flow cytometry for Ad hexon	Report Results	75% positive UAB QC-778	70% Positive UAB QC-868	X	X
Virus Burst Assay	Report Results	2,864 IU/viable cell plated, UAB QC-779	3010 IU/viable cell plated, UAB QC- 869	X	X
Viable cell count	Report Results	2.8×10^7 viable cells/vial, UAB QC-777	2.4×10^7 viable cells/vial, UAB QC- 867	X	X
Cell viability	> 70% viable	92% viable UAB QC-777	89% viable UAB QC-867	X	X
Sterility: USP <71>, 21 CFR610.12, EP2.6.1 and JP 4.06	No Growth	PASS / BioReliance, AE31BC.S10120G MP.BSV_CA	PASS, UAB QC-871	X	X
Endotoxin/LAL	< 5.0 EU/mL	PASS, <0.5 EU/mL, QC 755	PASS, <0.5 EU/mL, QC-870	X	X

